## Appendix IIF. Data Collection Tool For Home-based Sample Collection

### For all home-visits:

1. Participant ID \_\_\_\_\_
2. Date of visit \_\_\_\_\_
3. Person conducting visit \_\_\_\_\_
4. Reason for visit
  - a. Birth VL test
  - b. 6-month VL test
  - c. Other, please specify \_\_\_\_\_
5. How many times have study staff attempted to reach this participant through a home visit?
  - a. 1
  - b. 2
  - c. 3
  - d. 4 or more
6. Participant's status
  - a. Home
  - b. Not at home
  - c. Moved to different location
  - d. Deceased
7. Is anybody (other than the participant's infant) home?
  - a. Yes, participant's partner
  - b. Yes, participant's non-infant child or children
  - c. Yes, participant's other family member (please specify who \_\_\_\_\_)
  - d. Yes, participant's neighbor or friend
  - e. No, participant is alone
8. If YES (a, b, c, or d) to question 7: Has the participant disclosed her HIV status to all people who are currently at her home?
  - a. Yes
  - b. No
  - c. Unknown

**If anyone is home, other than the participant and her infant and she has not disclosed or her disclosure status is unknown, privacy and confidentiality may be compromised. Reschedule VL and EID test (if applicable) to ensure patient confidentiality. Proceed with "well-baby" visit (Questions 9-14).**

**If no-one is home, other than participant and her infant, OR she has disclosed her HIV status to everyone in the home, please proceed to questions 15 - 20**

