**Participant tracking for VL among participants 'lost to follow-up' (LTFU).** Measurement of viral suppression rates in either study arm can be skewed if detectable VL is more/less frequent in LTFU patients. Therefore, we will use a weighted sampling-based approach to track patients who receive no delivery VL test or postpartum VL test within 6 months. From a twice monthly LTFU patient list for each site, participants will be targeted for active tracking including phone calls and home visit to reach women who disengaged from care prior to or by the time of delivery, and thus had no VL sample collected at the time of delivery. Study staff conducting home visits (mentor mother and community health worker) will be thoroughly trained on protection of confidentiality, especially when participants are not home or have relocated. Visits will be introduced as well-baby visits to protect confidentiality, and a dried blood spot sample (DBS) for VL will only be collected once privacy is confirmed and consent provided. Visits will be rescheduled if privacy is perceived to be compromised at any time. Women whose infant has not yet tested for HIV will be offered sample collection for infant testing, and DBS will be transported for processing (Appendix 2F, Home Visit Survey).

**Objective 2 Outcomes.** The primary outcome for Objective 2 is the proportion of clients with a detectable VL at delivery and within 6 months postpartum. Given the ongoing shortage of VL testing in the country, all women who have not received a postpartum VL test by 6m postpartum will be offered a "study-initiated" VL test. These samples will be collected and shipped in the same manner as the delivery VL test and will be supported by study funds and sent to the KEMRI CDC lab for processing. Furthermore, at the 6m visit, infants will be offered an HIV PCR test, which will also be sent to KEMRI CDC lab. Participants who receive these "study-initiated" tests will not be considered "completely retained" for the aim 1 primary outcome; however, these data are necessary for the aim 2 outcome. Secondary outcomes associated with Objective 2 will include VL test coverage (proportion with VL test in antenatal and postpartum periods, per guidelines), VL

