Participants will be informed of these conditions during the informed consent process and the precautions described above will be employed to mitigate any risks to participant confidentiality, privacy, and safety.

**Intimate Partner Violence (IPV).** If a case of IPV is reported during study engagement (per routine surveys including questions to assess risk and experience of IPV), the participant will be counseled on options for seeking care and referred to the nearest service provider, including referral for legal action. Participants who report IPV over the phone (via study contact or mentor mother) will be encouraged to visit the clinic for an in-person consultation and will also be offered a home visit by a mentor mother. All study staff will be trained to ask for and identify signs of IPV among pregnant and postpartum women living with HIV. Any form of IPV during the study period will be reported as an adverse event.

**Psychological Distress.** The informed consent process will be carefully designed to prepare women for the Early Infant Diagnosis testing process after they deliver and the possibility of an HIV positive diagnosis for their infants. In addition, the existing use of peer counselors to support pregnant women and mothers to consider care and treatment options for themselves and their infants, and to process their and their infant's HIV positive diagnosis will continue to be employed in the study. If additional support and follow-up services are needed, the PMTCT/EID provider will arrange for additional on-site counseling.

**Reduction of Physical pain and/or discomfort.** Dried blood spot (DBS) samples will be collected for all research-related viral load testing. Providers are most experienced with this form of blood sample collection and thus may be more proficient in collecting samples in this manner with less pain and discomfort for the participant. Training on VL testing procedures will be reinforced to minimize risk of collection errors and need for repeat sample collection.

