## Risk of Violence

For each of the following statements (21-24), choose the answer which best indicates how often each has occurred in the past 12 months.

|   | Never | Rarely | Sometimes | Frequently |
|---|-------|--------|-----------|------------|
| 21. In the past 12 months, has your partner ever insulted you or made you feel bad about yourself?                          |       |        |           |            |
| 22. In the past 12 months, has your partner ever hit you, kicked you, dragged you, or beaten you up?                        |       |        |           |            |
| 23. In the past 12 months, has your partner ever hit, kicked, dragged or beaten your child?                                 |       |        |           |            |
| 24. In the past 12 months, has your partner ever physically forced you to have sexual intercourse when you did not want to? |       |        |           |            |

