**Home visit for VL collection (if confidentiality is secure)**

15. Was VL sample collected..... Y / N

14a. If no, why not?

a. Participant refused

b. Other, please specify \_\_\_\_\_

16. Was the survey completed..... Y / N

a. If no, why not?

i. Participant refused

ii. Other, please specify \_\_\_\_\_

17. Where is the participant currently accessing HIV services for herself and her infant?

a. At the study hospital

b. At a different health care facility, please specify which \_\_\_\_\_

c. With a traditional healer

d. Disengaged from care

e. Other, please specify \_\_\_\_\_

18. Has the infant had his/her age-appropriate HIV test sample collected at a health care facility (6 wks or 6 months)?..... Y / N

19. **If yes to #18**, which facility \_\_\_\_\_

20. **If no to #18**, was an EID sample collected at the home visit? ..... Y / N

i. If no to #20, why not?

a. Participant refused

b. Infant was not at home

c. Other, please specify \_\_\_\_\_

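### The home-visit form clears a visit on HIV disclosure alone, so partner-violence questions may be asked with the partner at home and no rule that he be out of hearing

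*Combined protocol and SAP*

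**What the plan says.** All references are to the combined protocol and SAP.

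- **Appendix IIF, part for all home visits.** Question 7 asks who is home besides the infant, and its first option is "Yes, participant's partner". Question 8 asks: "Has the participant disclosed her HIV status to all people who are currently at her home". If someone else is home and "she has not disclosed or her disclosure status is unknown, privacy and confidentiality may be compromised", the viral load and infant tests are rescheduled and staff carry on with the well-baby questions. If no one else is home, "OR she has disclosed her HIV status to everyone in the home, please proceed to questions 15 - 20".
- **Appendix IIF, viral load collection block (questions 15 to 20).** Question 16 is "Was the survey completed".
- **Appendices IIB (items 21 to 24) and IIC (items 15 to 18), Risk of Violence.** These cover insults, physical violence against the woman or her child, and forced sex. One item reads: "In the past 12 months, has your partner ever hit you, kicked you, dragged you, or beaten you up". Both surveys also contain a self-harm item (IIB 20, IIC 14).
- **Objective 2 specific methods, tracking of participants lost to follow-up.** "Visits will be rescheduled if privacy is perceived to be compromised at any time".
- **Section 8.0, Intimate Partner Violence.** Reported violence leads to counselling and referral and is recorded as an adverse event. Women who report it by phone are encouraged to attend the clinic and "will also be offered a home visit by a mentor mother".

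**The concern.** The form uses one test, knowledge of HIV status, for two different risks. It suits the first, which is that a household member learns the woman's status from the visit. It says nothing about the second, which is that a woman is asked about her partner's violence while he can hear. The protocol itself treats partner violence as a risk separate from loss of confidentiality.

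The first stake is safety: a truthful answer given within the partner's hearing could provoke harm. The second is data quality: a woman who feels overheard may answer that violence never happened. These answers can feed adverse-event reporting, and the Participant surveys paragraph says the repeated measures are collected to study mediation and moderation.

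**Working it through.** No figure in the plan bears on this, so the check is a trace of the form's routing against the rest of the document.

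1. **Can the partner be home on a cleared visit?** Yes. Partner at home (7a) plus status disclosed to everyone present (8a) meets the condition to proceed. The stop rule needs someone else at home and status undisclosed or unknown, so it does not apply.
2. **Does the cleared block include the survey?** Yes, through question 16.
3. **Which survey is it?** Question 16 does not name it. The Participant surveys paragraph attaches the repeat surveys after delivery and at 6 months to viral load sample collection and says they repeat the enrollment measures, which include risk of violence. Section 6.0 lists interpersonal violence in the survey taken at the delivery and postpartum viral load tests, and says mentor mothers conduct it. The two named visit reasons on Appendix IIF are those same tests. The natural reading is Appendix IIB or IIC.
4. **Does any step on this path check hearing or defer the violence items?** None does. Question 7 records who is in the home, not who is within earshot. The reasons offered in question 16 for an incomplete survey are refusal and other.
5. **Does another section supply the missing condition?** The rescheduling rule under Objective 2 is general. In section 8.0 the same rule appears as protection against inadvertent disclosure of HIV status. The partner-violence paragraph covers counselling, referral, staff training and adverse-event reporting, but not the conditions for asking.
6. **Is the form consistent with itself?** No. The heading of the well-baby block gives the presence of another person as a trigger for that branch. The routing text sends an accompanied visit there only when status is undisclosed or unknown. With a status-aware partner at home, the two point to different branches.
7. **Is this a slip in the English form only?** No. The Swahili and Luo versions use the same disclosure test.

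**The case against.** The best defence is that staff are not bound to continue. They may reschedule whenever they perceive privacy to be compromised, which would cover a partner who comes within earshot. The cleared block is headed as applying when confidentiality is secure, samples are taken only once privacy is confirmed, and all study staff are trained to ask about partner violence and recognise its signs. Question 16 also accepts that the survey was not completed. All of this stands. A reader might infer that the form orders staff to put these questions in front of the partner. It does not. It permits the situation and leaves prevention to judgement, without saying that the violence items call for it.

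The survey in question 16 could instead be the home-visit form itself, which the Objective 2 text calls a home visit survey. That is possible but strained, because a form would then be asking whether it had been completed.

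A reader might also infer that women who report violence by phone will be surveyed at the home visit they are offered. Appendix IIF is meant for all home visits and has an open reason field, but nothing links Appendix IIB or IIC to that support visit.

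Finally, the consent pages are not in the text reviewed, so any privacy wording there could not be checked.

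**Conclusion.** The gap is real. Following the form as written can lead to partner-violence questions with a status-aware partner at home, and no section requires that he be out of hearing. The conclusion rests on reading question 16 as Appendix IIB or IIC. The safety argument needs no count of visits.

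Two stronger readings are tempting, and the documents support neither.

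- **A count of affected visits.** One could take the 24% loss to follow-up by delivery and the planned 1,452 women: 0.24 × 1,452 ≈ 348. But the 24% comes from one pilot control site. Women lost to follow-up are not the same as home visits, since tracing uses a sampling-based approach and phone calls as well as visits. The share with a status-aware partner at home is not given. Any count would rest on an invented proportion.
- **Bias between arms.** One could argue that control sites will have more home visits and so more under-reporting. Better retention at intervention sites is the trial's hypothesis, but unequal home visiting is not a stated expectation. The plan's own viral load adjustment uses the same loss in both arms: 1 + 0.24 × 0.5 = 1.12, giving 31.3% × 1.12 ≈ 35% and 9.1% × 1.12 ≈ 10.2%.

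Violence is neither a primary nor a listed secondary outcome, and it is not among the individual-level factors named in the Objective 1 analysis. Any distortion would fall on adverse-event capture and exploratory analyses, not on the primary efficacy comparisons.

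**What to change.** 1. Reconcile the routing text in Appendix IIF with the heading of the well-baby block, so that an accompanied visit has one path.
2. Keep the HIV-disclosure rule for sample collection.
3. Add a check, in English, Swahili and Luo, that the Risk of Violence items (IIB 21 to 24, IIC 15 to 18) and the self-harm item (IIB 20, IIC 14) are asked only when the woman is out of hearing of others. Otherwise defer them to a private phone or clinic contact. Leave the partner-support items outside this restriction: partner support is a named covariate, and withholding it whenever a child or neighbour is home would add missing data.
4. Add a question 16 code for sensitive items deferred because the setting was not private.
5. State in the analysis plan that deferred items not later obtained are missing and are never coded as no violence.

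The cost is a form and training amendment, some missing or delayed answers and, for some women who are already hard to trace, one more contact attempt.

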### Well Baby Visit (if other person is present/confidentiality is compromised):

9. Baby's MUAC \_\_\_\_\_ cm
10. Baby's temperature \_\_\_\_\_ ° Celcius
11. How is breastfeeding going?
  - a. Good
  - b. Fair
  - c. Poor
12. Any concerns with breastfeeding? \_\_\_\_\_  
\_\_\_\_\_  
\_\_\_\_\_
13. Any concerns with baby's health? \_\_\_\_\_  
\_\_\_\_\_  
\_\_\_\_\_

14. Any concerns with your own health? \_\_\_\_\_

**Home visit for VL collection (if confidentiality is secure)**

15. Was VL sample collected..... Y / N

14a. If no, why not?

a. Participant refused

b. Other, please specify \_\_\_\_\_

16. Was the survey completed..... Y / N

a. If no, why not?

i. Participant refused

ii. Other, please specify \_\_\_\_\_

17. Where is the participant currently accessing HIV services for herself and her infant?

a. At the study hospital

b. At a different health care facility, please specify which \_\_\_\_\_

c. With a traditional healer

d. Disengaged from care

e. Other, please specify \_\_\_\_\_

18. Has the infant had his/her age-appropriate HIV test sample collected at a health care facility (6 wks or 6 months)?..... Y / N

19. **If yes to #18**, which facility \_\_\_\_\_

20. **If no to #18**, was an EID sample collected at the home visit? ..... Y / N

i. If no to #20, why not?

a. Participant refused

b. Infant was not at home

c. Other, please specify \_\_\_\_\_

**Kiambatisho IIA. Maswali ya Usajili kwa mgonjwa**

**Kujazwa na Muuliza maswali:**

Nambari ya usajili: \_\_\_\_\_

Tarehe ya mahojiano \_\_\_\_\_

Majina ya muuliza maswali kwa kifupi (Initials of interviewer) \_\_\_\_\_

**Demografia ya mama:**

1. Tarehe ya kuzaliwa kwa mama: \_\_\_\_\_
2. Nambari ya simu ya mama: \_\_\_\_\_
3. Maelezo ya jinsi mama anaweza kufikiwa:  
\_\_\_\_\_
4. Tarehe ya kwanza ya ujisajili katika huduma za PMTCT: \_\_\_\_\_
5. Makadirio ya tarehe ya kujifungua: \_\_\_\_\_
6. Tarehe uliyo anzishwa huduma za HAART: \_\_\_\_\_
7. Kiwango chako cha juu zaidi cha elimu ni?
  - a. Sina elimu (no formal education)
  - b. Sikumaliza shule ya msingi
  - c. Nilihitimu shule ya msingi
  - d. Sikumaliza sekondari
  - e. Nilihitimu sekondari
  - f. Sikumaliza chuo kikuu
  - g. Nilihitimu chuo kikuu
8. Ni nani umemfahamisha kuhusu hali yako ya VVU?
  - a. Hakuna
  - b. Mchumba/Mume
  - c. Mmoja au zaidi katika familia
  - d. Rafiki/Marafiki
  - e. Mzazi/Wazazi
9. Je, wewe hufikiaje simu ya rununu?
  - a. Nina yangu mwenyewe
  - b. Natumia na mtu anayefahamu hali yangu ya VVU
  - c. Natumia na mtu asiye fahamu hali yangu ya VVU
  - d. Mimi huomba mtu simu ninapohitaji
  - e. Sina njia ya mawasiliano ya simu ya rununu
10. Je, hukuchukua mda gani kufika hospitalini (Dakika) \_\_\_\_\_
11. Gharama za kwenda hospitalini (kuenda na kurudi, KES) \_\_\_\_\_
12. Je, hali yako ya uhusiano ikoje?
  - a. Sijaoa
  - b. Nimeolewa
  - c. Sijaoa lakini niko katika uhusiano
  - d. Nimeachana na mchumba/mume (separated)
  - e. Nimepewa talaka (Divorced)
  - f. Ni Mjane
  - g. Ingingine, fafana \_\_\_\_\_
13. Je, hali yako ya maisha ikoje?
  - a. Sina mpenzi kwa hivi
  - b. Ninaishi kando na mchumba/mume
  - c. Ninaishi na mchumba/mume
14. Una watoto wangapi?
  - a. Uliowazaa mwenyewe \_\_\_\_\_

b. Waliozaliwa na mwingine \_\_\_\_\_

15. Je, umewahi kupata huduma za PMTCT/EID mbeleni? .....Ndio/Hapana

Usaidizi toka kwa mpenzi, na maamuzi kuhusu fedha

16. Je, hali ya VVU ya mchumba wako ikoje?

- a. Ana VVU
- b. Hana VVU
- c. Sijui
- d. Sina mpenzi kwa sasa

17. Je, mpenzi wako alichukulia vipi habari za ujauzito wako?

- a. Alikuwa na raha
- b. Alikua vugu vugu (Neutral)
- c. Hakuwa na raha
- d. Sijui
- e. Sina mpenzi kwa sasa

18. Kwa kawaida, ni nani hufanya uamuzi wa matumizi ya pesa katika boma yako?

- a. Mchumba wangu, kila mara
- b. Mchumba wangu zaidi kuniliko
- c. Sote, kwa usawa
- d. Mimi, mara nyingi kuliko mwenzi wangu
- e. Mimi, kila mara
- f. Sina mpenzi kwa sasa

19. Mapato yako ya wastani katika boma lako kila wiki ni?

- a. Chini ya 500 KES
- b. 500-750 KES
- c. 750-1,000 KES
- d. 1,000-2,500 KES
- e. Zaidi ya 2,500 KES

20. Nina wasiwasi kuwa sitakuwa na pesa za kutosha kunifikisha hospitalini kwa hudum zangu, au za mtoto wangu

- a. Nakubali kabisa
- b. Nakubali
- c. Sikubali
- d. Sikubali kabisa

Usaidizi wa mchumba/Mpenzi

21. Je, kuna umuhimu kwako kwa mchumba wako kukuunga mkono katika taaribu zifuatazo?

|  | Sio muhimu kabisa | Sio muhimu sana | Muhimu | Muhimu sana | Sina mchumba/Haihusiani |
|--|-------------------|-----------------|--------|-------------|-------------------------|
| 21a. Kuhudhuria taratibu zako za PMTCT na wewe?                                      |                   |                 |        |             |                         |
| 21b. Kukupa pesa za usafiri kwenda hospitalini?                                      |                   |                 |        |             |                         |
| 21c. Kukupa ushauri wa jinsi ya kuishi kwa afya ukiwa mja mzito?                     |                   |                 |        |             |                         |
| 21d. Kukusaidia majukumu ya nyumbani ili uweze kupumzika?                            |                   |                 |        |             |                         |
| 21e. Kuku saidia na majukumu ya nyumba, ili uweze kuhudhuria taratibu zako za PMTCT? |                   |                 |        |             |                         |
| 21f. Kukukumbusha kumeza dawa zako?  |                   |                 |        |             |                         |
| 21g. Kukukumbusha umuhimu wa kufuata maagizo ya daktari                              |                   |                 |        |             |                         |
| 21h. Kutoa pesa za kununua dawa au vitamini?   |                   |                 |        |             |                         |

|   |  |  |  |  |  |
|---|--|--|--|--|--|
| 21i. Kuhudhuria wakati wa kuzaliwa kwa mtoto? |  |  |  |  |  |
|---|--|--|--|--|--|

22. Je, ni kwa nanma gani unatarajia mchumba wako kukusaidia wakati wa uja uzito?

|  | Sitarajii | Sina uhakika | Natarajia | Sina mchumba/
Hainihusu |
|--|-----------|--------------|-----------|----------------------------|
| 22a. Kuhudhuria taratibu zako za PMTCT na wewe?                                |           |              |           |                            |
| 22b. Kukupa pesa za usafiri kwenda hospitalini?                                |           |              |           |                            |
| 22c. Kukupa ushauri wa jinsi ya kudumisha afya ukiwa mja mzito?                |           |              |           |                            |
| 22d. Kukusaidia na majukumu ya boma ili uweze kupumzika?                       |           |              |           |                            |
| 22e. Kuku saidia na majukumu ya boma ili uweze kuhudhuria taratibu zako PMTCT? |           |              |           |                            |
| 22f. Kuku kumbusha kumeza dawa zako?   |           |              |           |                            |
| 22g. Kukukumbusha umuhimu wa kufuata maagizo ya daktari?                       |           |              |           |                            |
| 22h. Kukupa pesa za kununua dawa au vitamini?                                  |           |              |           |                            |
| 22i. Kuhudhuria wakati wa kuzaliwa kwa mtoto?                                  |           |              |           |                            |

#### Mawazo

Tafadhali chagua jibu linalo karibiana na jinsi ulivyokuwa ukihisi wiki moja iliyopita, sio leo tu.

23. Ninatazamia maisha ya furaha
  - a. Zaidi ya kawaida
  - b. Kidogo, kuliko kawaida
  - c. Kidogo sana, kuliko kawaida
  - d. La
24. Nime jilaumu bila sababu wakati mambo yameenda vibaya
  - a. Ndio, mara nyingi
  - b. Ndio, wakati mwengine
  - c. La, sio sana
  - d. La, sijawahi
25. Nimehisi hofu na wasiwasi bila sababu ya maana
  - a. Ndio, mara nyingi
  - b. Ndio, wakati mwengine
  - c. La, sio sana
  - d. La, sijawahi
26. Nimekuwa bila furaha hadi nimekuwa nikilia
  - a. Ndio, mara nyingi
  - b. Ndio, wakati mwengine
  - c. La, sio sana
  - d. La, sijawahi
27. Nimekuwa na mawazo ya kujiumiza mwenyewe
  - a. Ndio, mara nyingi
  - e. Ndio, wakati mwengine
  - f. La, sio sana
  - g. La, sijawahi

